3.2 Sample Size

Approximately 64 DLT evaluable subjects will be enrolled in this phase 1b study.

In Part 1, at least 3 **DLT-evaluable** subjects will be enrolled for each of the oprozomib formulations. In Part 2, a Bayesian design will be applied to evaluate the oprozomib formulations (IR and GR) administered at increasing dose levels in combination with pomalidomide and dexamethasone. The maximum sample size for testing the IR formulation is set to

36 DLT evaluable subjects. The anticipated sample size under the assumption of 11 cohorts evaluated for the GR formulation is 22 DLT evaluable subjects.

[figure not shown]
For United States: for the roll-over portion of the study, the sample size for this study cannot be determined prospectively, as it is contingent on the number of subjects completing previous studies, or having clinical benefit but not otherwise being able to continue the previous oprozomib study.

4. Covariates and Subgroups

4.1 Planned Covariates

No covariate or subgroup is pre-specified for the analysis of the primary, secondary, and safety endpoints. The relationship of covariates to efficacy endpoints will be explored if appropriate.

4.2 Subgroups

5. Definitions

Age at Enrollment

Subject age at enrollment will be determined using the age in years reported in the clinical database.

Baseline

For any variable, unless otherwise specified the baseline is the last assessment taken prior to the first administration of study treatment. For parameters/assessments not scheduled to be performed (or scheduled but not performed) on the same day as the

first administration of study treatment, the baseline value is the value from the screening period measured closest to the day of first administration of study treatment.

Baseline and Post-Baseline ECG Values in Triplicate

The baseline ECG is defined as the mean of all pre-dose assessments; the mean of values in a triplicate should be calculated before taking the mean of the triplicate averages.

For all post-baseline ECG, the mean value for measurements taken at the same assessment will be calculated and used in the analysis.

For pre and post dose ECG measurements, unscheduled ECG measurements taken up to 5 minutes after the last assessments of a triplicate will be included in the average for a timepoint. Where an ECG is missing within a triplicate, all available data will be averaged for that timepoint.

Bazett-corrected QT Interval (QTcB)

The Bazett correction will be calculated from the investigator reported QT (msec) and RR interval (msec), as follows: $QTcB=QT/(RR/1000)^{1/2}$

Change From Baseline

Change from Baseline is the arithmetic difference between post-dose assessments and Baseline value.

Change (absolute) from Baseline=(Post-baseline Value – Baseline Value)

Change (percent) from Baseline=[(Post-baseline Value – Baseline Value)/Baseline Value]x100

Dose Limiting Toxicities (DLT) Window

The DLT window will be the initial 28 days of study treatment. The DLT window may be extended to assess events starting within the window in case the DLT definition is time dependent. Any adverse event occurring outside the DLT window that is determined by the investigator to be possibly related to the investigational product, which is seen more frequently or is more severe than expected or is persistent despite appropriate management, can be determined to be a DLT upon unanimous decision by the DLRT after review of the adverse event and all available safety data.

DLT Evaluable

In order to be DLT-evaluable, a subject would receive the doses of study treatment as specified below during the 28 day DLT window:

- All planned doses of oprozomib must be received
- A minimum of 17 of 21 planned doses of pomalidomide must be received
- A minimum of 6 of 8 planned doses of dexamethasone must be received

If the subject discontinues the treatment or misses a dose of oprozomib for reasons other than DLT before completion of the DLT window, the DLRT will decide if the subject is DLT-evaluable and will make the final decision on subject replacement.

Duration of Response (DOR)

Duration of response is defined as the number of days between the date of the first tumor assessment indicating an objective response through to the subsequent date of progression or death due to any cause, or where applicable date of censoring [date of first progressive disease assessment or death or date of censoring – date of the first objective response result +1]. Subjects who respond and have not progressed while on study will be censored at the date of assessment of the last evaluable tumor assessment. Subjects who do not achieve an objective response will be excluded from the analysis of duration of response. Objective response is defined as any of the following: stringent complete response (sCR), complete response (CR), very good partial response (VGPR), or partial response (PR) (all according to Revised International Myeloma Working Group Uniform Response Criteria [IMWG-URC]).

Enrollment Date

Enrollment Date is defined as the date when the dosing of investigational product (oprozomib) is started.

Fridericia-corrected QT Interval (QTcF)

The Fridericia correction will be calculated from the investigator reported QT (msec) and RR interval (msec), as follows: $QTcF=QT/(RR/1000)^{1/3}$

Use above definition for derivation only if QTcF is not collected in the CRF.

Investigational Product

The term 'investigational product' is used in reference to oprozomib.

Study Treatment

Any combination of oprozomib, pomalidomide and dexamethasone, **or monotherapy of oprozomib.**

Last Investigational Product Dose Date

The last IP dose date for each subject is defined as the latest date IP is administered.

Maximum Tolerated Dose (MTD)

MTD for each formulation is defined as the dose that has the highest posterior probability of having a DLT rate within the target toxicity interval (15% to 25%), while the posterior probability of excessive/unacceptable toxicity (> 25% to 100%) is < 40%

Study Day 1

It is defined as the first day that protocol specified study treatment is administered to the subject.

Study Day

Post study day: study day= (date - date of Study Day 1) + 1

Pre study day: study day= (date – date of Study Day 1)

Time to Response (TTR)

Time to response defined as the interval from the first administration of study treatment to the first documentation of confirmed response. Response is defined as any of the following: stringent complete response (sCR), complete response (CR), very good partial response (VGPR), or partial response (PR) (all according to Revised International Myeloma Working Group Uniform Response Criteria [IMWG-URC]).

Time to response is calculated as the number of days:

(date of first response – date of study day 1 +1).

Time to response will be calculated only for subjects with response.

Treatment-Emergent Adverse Event (TEAE)

Treatment-emergent adverse events are events categorized as Adverse Events (AEs) **starting on or after first dose of investigational product as determined by the flag indicating if the adverse event started prior to the first dose on the Events CRF and up to and including 30 days after the last dose of investigational product or the End of Study date, whichever is earlier.**

Treatment-Related AE

A treatment-related AE is any treatment-emergent AE that per investigator review has a reasonable possibility of being caused by study treatment.

Disease-Related Events

Disease-Related Events are events (serious or non-serious) anticipated to occur in the study population due to the underlying disease.

C_{max}

Maximum observed serum concentration.

t_{max}

Time to C_{max}

AUC_{last}

Area under the concentration-time curve from time 0 (time of investigational product administration) to the time of the last quantifiable concentration.

Progression free survival

The number of months from subject's first study dose date to the earlier of disease progression or death due to any cause.

Progression free survival data will be censored as described below:

- **Patients who are alive and do not have documented disease progression at the time of analysis will be censored at the date of the last disease assessment.**
- **Patients who are alive and do not have disease assessment at the time of analysis will be censored at the first study dose date.**
- **Patients who are alive without documented disease progression, and have withdrawn consent at the time of analysis will be censored at the date of the last disease assessment before withdrawal of consent.**
- **Patients who have started an anti-cancer therapy other than the study treatment prior to documentation of disease progression will be censored at the date of the last disease assessment prior to start of new therapy.**

Best Overall Response (BOR)

The best response that a subject achieved during study where the responses are ranked from best to worst as follows: stringent complete response [sCR], complete response [CR], very good partial response [VGPR], and partial response [PR], minimal response [MR], stable disease [SD] and progressive disease [PD] (all according to Revised International Myeloma Working Group Uniform Response Criteria [IMWG-URC])

Overall Response Rate (ORR)

Proportion of subjects with BOR of sCR, CR, VGPR or PR.

Duration of Grade II GI Toxicity

Duration of Grade II GI toxicity is defined as the number of days between the start date through to the subsequent end date of the Grade II GI toxicity, or where applicable date of censoring [end date of the Grade II GI toxicity or date of censoring – start date of the Grade II GI toxicity +1]. Subjects whose Grade II GI toxicity do not end while on study will be censored at the date when they are last on study. Subjects who do not experience Grade II GI toxicity will be excluded from the analysis of duration of Grade II GI toxicity. **The intermittent adverse events will be excluded from the analysis of duration of Grade II GI toxicity, and not to be counted as one ongoing adverse event.**

Duration of Grade III or above GI Toxicity

Duration of Grade III or above GI toxicity is defined as the number of days between the start date through to the subsequent end date of the Grade III or above GI toxicity, or where applicable date of censoring [end date of the Grade III or above GI toxicity or date of censoring – start date of the Grade III or above GI toxicity +1]. Subjects whose Grade III or above GI toxicity do not end while on study will be censored at the date when they are last on study. Subjects who do not experience Grade III or above GI toxicity will be excluded from the analysis of duration of Grade III or above GI toxicity. The intermittent adverse events will be excluded from the analysis of duration of Grade III or above GI toxicity, and not to be counted as one ongoing adverse event.

Non-roll over subjects

Subjects that were enrolled into this study and do not participate in the open-label roll-over part of the study will be referred to as “non-roll over subjects”.

Roll-over subjects

Subjects that were previously treated on a separate Amgen protocol and participate in the open-label roll-over part of the study will be referred to as “roll-over subjects”.

6. Analysis Sets

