#### 13.4.3.2 Efficacy Endpoints

All efficacy assessments will follow IMWG uniform response criteria and be performed every 4 weeks ( $\pm$  1 week).

Overall response rate (defined as the proportion of best overall response of stringent complete response [sCR], complete response [CR], very good partial response [VGPR], and partial response [PR]), best overall response, PFS (defined as the number of months from subject's first study dose date to the earlier of disease progression or death due to any cause), and DOR will be summarized for all subjects overall, by formulation, by dose cohort level, and by formulation and dose cohort level along with 95% confidence intervals when applicable.

All subjects who receive treatment with any amount of the OPomd and have a baseline disease assessment and at least 1 post-baseline disease assessment will be included in the efficacy analyses. Additional efficacy analyses will be performed based on subjects who receive treatment with any amount of OPomd.

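### The DOR censoring sentence does not require the responder to be alive, so a death on study without progression is both an event and censored

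*SAP*

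**What the plan says.** All the relevant rules stand in SAP section 5, Definitions.

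- **DOR, event clause.** DOR runs from the first objective response "through to the subsequent date of progression or death due to any cause, or where applicable date of censoring". The bracketed formula that follows gives the end date as the "date of first progressive disease assessment or death or date of censoring". It states no order of precedence among the three.
- **DOR, censoring sentence.** "Subjects who respond and have not progressed while on study will be censored at the date of assessment of the last evaluable tumor assessment". This is the only DOR sentence that says who is censored.
- **PFS, for comparison.** The first PFS censoring rule reads "Patients who are alive and do not have documented disease progression at the time of analysis will be censored", and the third reads "Patients who are alive without documented disease progression, and have withdrawn consent at the time of analysis will be censored". The second also applies only to living patients. The SAP's change log records these PFS rules as added in Amendment 1 and lists no change to the DOR sentence.

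Outside section 5 there is nothing more specific. Protocol section 13.4.3.2 says that "DOR will be summarized for all subjects overall, by formulation, by dose cohort level" and by the combination of the two. SAP section 9.5.2 repeats that wording. Neither gives an event rule or a censoring rule for DOR.

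**The concern.** A responder who dies on study without documented progression satisfies both DOR rules at once. The event clause says the response ended at death. The censoring sentence says the subject is censored at an earlier date. A programmer who codes the censoring sentence as written would remove the death from the DOR events.

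Two things follow. First, death during response would be handled as if it carried no information about how long the response would have lasted, which tends to make DOR look longer than it was. Second, DOR and PFS would disagree about the same subject. The death is a PFS event (unless new anti-cancer therapy had been started first), while DOR is censored.

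DOR is a secondary endpoint, and efficacy data are among the data the DLRT reviews when it recommends a formulation and dose (SAP section 3.1; protocol section 9.2.1.2). Responders per formulation and dose cohort are few, so a single reclassified death can visibly change a DOR curve.

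**Working it through.** No sample size, power or error rate in the plan depends on this sentence, so there is no stated figure to reproduce. The check has four steps.

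**1. Classify each outcome of a responder under the two DOR sentences.**

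| Outcome | Event clause | Censoring sentence | Consistent? |
|---|---|---|---|
| Progressed on study | Event | Not covered | Yes |
| Alive, not progressed | No event | Censored | Yes |
| Died on study, not progressed | Event at death | Censored at last evaluable assessment | No |

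Only the third row conflicts.

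**2. Apply the SAP's formula (end date − first response date + 1) to that row.** The days are assumed: first response day 57, last evaluable assessment day 113, death without progression day 130.

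- Event reading: 130 − 57 + 1 = 74 days, event.
- Censoring reading: 113 − 57 + 1 = 57 days, censored.

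Both the duration and the event indicator change.

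**3. Direction of the effect on a Kaplan-Meier curve.** Suppose R responders are at risk at the last assessment of the subject who dies, k others have events between that assessment and the death, and nobody else is censored in that interval. Up to and including the death, the curve is multiplied by:

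- event reading: (R − k − 1)/R;
- censoring reading: (R − 1 − k)/(R − 1).

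The second is at least as large as the first, so from the death onward the censoring reading is never lower. With R = 3 and k = 0 the factors are 2/3 and 2/2 = 1. Between the last assessment and the death the censoring reading can be lower, because the risk set is one smaller. *Tends to overstate* is therefore the right strength of claim.

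The median is less predictable. Assume three responders with distinct end times t1 < t2 < t3. If all three are events, the curve falls to 2/3, 1/3 and 0, and the median is t2. Now censor one of them as a death:

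- The earliest is censored: two are at risk at t2, so the curve is exactly 1/2 there. The median is t2, unchanged, if defined as the first time the curve is at or below 0.5. It is (t2 + t3)/2 under an averaging convention.
- The middle one is censored after t1: the curve is 2/3 until t3, and the median moves to t3.
- The middle one is censored before t1: two are at risk at t1, so the curve is 1/2 there. The median is t1 or (t1 + t3)/2, depending on the convention.

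The SAP states no convention for the median.

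**4. How many records could be affected.** Protocol section 5.5.5 reports responses (PR or better) with OPomd in 20 of 28 evaluable IR subjects and 3 of 8 evaluable GR subjects, that is 20 + 3 = 23 responders. Table 2 shows one fatal adverse event and one fatal disease-related event, both in OPomd GR 200 mg (N = 5). The documents do not say whether these are one or two subjects, whether they had responded, or whether they had already progressed. The GR responders are not split by dose. These deaths therefore affect between 0 and 2 DOR records. Deaths outside the treatment-emergent window are not tabulated.

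**The case against.** The best defence is that the definition already settles the matter. Death is named as an end point twice, and censoring enters only where it applies. Since DOR ends at progression, death can be the end point only for a responder who has not progressed. If every such death on study were censored, the clause "through to the subsequent date of progression or death due to any cause" would have almost no use for death. On this view censoring applies only when neither end point has occurred, and the wording is merely loose.

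That is probably what was intended. It does not remove the conflict, because the one sentence that says when censoring applies names progression and omits death. The PFS rules in the same section show that the condition can be stated in a few words.

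Three further points against the concern stand and limit it:

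- **No affected subject is shown.** A reader might infer from the GR 200 mg deaths that GR durations of response are overstated. The documents do not support that: response and progression status of those who died is not given. Protocol section 12.1.1 counts death from myeloma among disease-related events, so progression may have come first.
- **The median need not move later.** A reader might infer that censoring a death always lengthens the median. As shown above, it depends on the data and on the convention used.
- **No formal comparison of formulations is planned.** A reader might infer that a formulation test is biased. The plan describes the analyses as hypothesis generating and mostly descriptive, and the choice of dose and formulation rests on all escalation data.

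The parallel with PFS is also incomplete. The fourth PFS rule, for new anti-cancer therapy, has no condition on being alive, and DOR has no such rule at all. That is a separate difference, which the change proposed here does not address.

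**Conclusion.** The DOR rule is wrong as written, and the point is minor. For a responder who dies on study without progression, the SAP gives two incompatible statuses and two different dates. Read literally, the censoring sentence contradicts the event clause, departs from the first three PFS censoring rules, and would tend to overstate DOR.

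The size in this trial is unknown. It rests on whether any responder died on study without progression, and for the deaths in Table 2 the range is 0 to 2 records. The MTD rule, the sample size and all error rates are unaffected. Because the final analysis is to use the same methods as the primary analysis (SAP section 7.3; protocol section 13.3.3), the ambiguity carries forward unless it is corrected.

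**What to change.** In the DOR censoring sentence of SAP section 5, insert only the words *are alive and*, so that it covers subjects who respond, are alive and have not progressed while on study. Leave the rest of the sentence, including the restriction to time on study and the censoring date, unchanged. Each outcome then has one status: progression is an event, death without progression is an event at the date of death, and a living responder without progression is censored at the last evaluable assessment. In the assumed example the result is 74 days with an event.

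Also check which reading the primary analysis programmed. If deaths without progression were censored, rerun DOR and say so in the report.

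The cost is three inserted words and a programming check. DOR may become slightly shorter.

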6.1 Safety Analysis Set

The safety population for roll-over subjects is defined as all roll-over subjects who receive any amount of oprozomib and/or dexamethasone.

6.2 Efficacy Analysis Set

The efficacy population is defined as subjects, **excluding roll-over subjects**, who are included in the safety evaluable population, and have a baseline disease assessment and at least 1 post-baseline disease assessment.

6.3 Pharmacokinetic Analyses Set

PK population is defined as subjects for whom at least 1 PK parameter can be adequately estimated, **excluding roll-over subjects**.

7. Planned Analyses

7.1 Interim Analysis and Early Stopping Guidelines

Non-roll over subjects:

No formal interim analysis will be conducted. Safety data will be reviewed on an ongoing basis. Amgen, in consultation with the site investigator, will review in Dose Level Review Meetings (DLRMs) all available cumulative data by cohort prior to making dose escalation decisions. **The database will not be cleaned and an as-is snapshot of the database will be used in the analyses.** Adverse events and DLTs observed in all subjects will be evaluated continually and fully integrated into all DLRMs and considered in all enrollment and dosing decisions.

7.2 Primary Analysis

Non-roll over subjects:

The main objectives of the primary analysis are to determine the MTD for each formulation of oprozomib in combination with pomalidomide and dexamethasone and further evaluate the safety, tolerability and efficacy of the OPomd combination in subjects with relapsed or refractory multiple myeloma. In addition, this analysis will be used to possibly recommend the most appropriate oprozomib dose and formulation to be tested in future clinical trials in an OPomd combination. The selection of the oprozomib

recommended dose and formulation will be based on all data from the escalation cohorts.

Safety and tolerability will be assessed through summaries of study drug administration, DLTs, adverse events, changes in selected laboratory analytes, vital signs, and physical findings by dose level. Means and standard deviations will be used to summarize the total dose for each component of study drug received. All summaries will be presented by the assigned dose level and for all subjects.

All adverse event data will be listed by study site, dose level, subject identification number, and study day. All adverse events will be summarized by preferred term, appropriate thesaurus levels, and CTCAE (Version 4.03) toxicity grade. In addition, all serious adverse events, including deaths, will be listed separately and summarized.

Efficacy analyses of ORR and BOR will be performed using both the efficacy and safety population as defined previously.

Roll-over subjects: the main objective of the primary analysis of roll-over subjects is to evaluate the safety profile for all subjects on continued oprozomib treatment. Safety profile will be presented through descriptive statistics of safety data (treatment-emergent serious adverse events, treatment-emergent adverse events).

The primary analysis will be based on subject data collected up to two months from the date of last subject enrollment. **All available data up to and including the data cutoff date will be cleaned and a locked database will be used in the analysis.**

